#### 6.1.1. Inclusion Criteria

Patients may be included in the study if they meet all of the following criteria during screening prior to first dose of study drug.

- [1] Have a confirmed diagnosis of advanced, refractory breast or prostate cancer that is evaluable by radiologic testing. Patients must have experienced tumor progression on or treatment intolerance to at least one prior therapy for their cancer and have declined or are ineligible for a standard treatment.
- [2a] For patients with metastatic castrate-resistant prostate cancer (CRPC) only:
  - a) must continue ongoing androgen deprivation therapy (gonadotropin-releasing hormone [GnRH] agonist or antagonist) with castrate levels of serum testosterone <50 ng/dL determined within 4 weeks prior to starting treatment;
  - b) if receiving an antiandrogen as part of first-line hormonal therapy, must have shown progression of disease off the antiandrogen prior to enrollment;
  - c) must be willing to continue androgen deprivation therapy while on study, if no prior orchiectomy;

- d) must meet at least 1 of the following 3 criteria for progressive metastatic disease, according to PCWG2 criteria:
  - i. a rise in prostate-specific antigen (minimal value 2 ng/mL;  $\geq 3$  consecutive rising values), or
  - ii.  $\geq 2$  new metastases on transaxial imaging or radionuclide bone scan, or
  - iii. soft tissue progression;
- e) replacement hormone therapy (including prednisone or equivalent up to 10 mg/day) initiated before study entry is permitted per Section 7.5.

[2b] For patients with breast cancer only:

- a) may continue ongoing antiestrogen therapy (for example, an aromatase inhibitor),
- b) replacement hormone therapy initiated before study entry is permitted per Section 7.5, and
- c) may continue ongoing trastuzumab therapy.

[3] Are  $\geq 18$  years of age.

[4] Have given written informed consent prior to any study-specific procedures.

[5] Have adequate organ and hematologic function, including:

- Hepatic: Bilirubin  $\leq 1.5 \times$  the upper limit of normal (ULN), and ALT and AST  $\leq 3.0 \times$  ULN. For patients with tumor involvement of the liver, AST and ALT  $\leq 5.0 \times$  ULN are acceptable. For patients with tumor involvement of the bone, alkaline phosphatase  $\leq 5.0 \times$  ULN is acceptable.
- Renal: Serum creatinine  $\leq 2.0 \times$  ULN.
- Absolute neutrophil count (ANC)  $\geq 1.0 \times 10^9/L$ .
- Hemoglobin  $\geq 9$  g/dL (5.58 mmol/L).

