## 10.8. Efficacy Analyses

Tumor response data will be reported using listings and descriptive statistics. The ORR is estimated by the proportion of enrolled patients who have a best overall response of complete response (CR) or partial response (PR). The disease control rate (DCR) is estimated by the proportion of enrolled patients who have a best overall response of CR, PR, or stable disease. A 95% exact confidence interval will be constructed to determine the level of precision of the ORR and DCR if appropriate. Time-to-event variables such as progression-free survival (PFS), duration of response, and overall survival (OS) will be tabulated if appropriate. The Kaplan-Meier method (Kaplan and Meier 1958) will be used to estimate the survival curves, medians, and survival rates at specified time points, if applicable.

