## Baseline and Cycle 1 Assessments (for All Dosing Schedules)

Procedure	Baseline Relative Day Prior to Day 1 of Cycle 1			Treatment Cycle 1 only					Comments	
	≤28	≤14	≤7	Day 1	Day 8	Day 15	Day 22	Day 29	Day 36	
	Except for the Cycle 1, Day 1 visit, allowable visit windows are ±3 days, unless indicated otherwise.									
Eligibility Assessments										
Informed consent	X									
Medical history		X								
β-hCG Pregnancy test			X							At baseline, a urine or serum pregnancy test is required for WOCBP. Thereafter, every 12 weeks after the first dose or according to local regulations, whichever is more frequent.
ECG		X			X			X		Note that in cases where ECG and blood sample collection are scheduled at the same time, all blood sampling should be performed prior to ECG assessment.
ECOG PS assessment		X		X	X	X	X	X		
Safety Assessments										
Physical examination		X		X		X		X		Includes height (at baseline only), and thoracic, abdominal, and symptom-directed examination.
Vital signs and weight measurement		X		X	X	X	X	X		Vital signs include temperature, pulse rate, respiration rate, and blood pressure. Vital signs will be checked and recorded prior to each infusion of LY3022855, midway through each infusion, at the end of each infusion, and every 15 minutes for the first hour following each infusion, including Cycle 1, Day 1 (also to be checked and recorded at nontreatment visits during Cycle 1).
Toxicity/AE assessment		X		X	X	X	X	X		Any preexisting toxicity should be documented, recorded, and graded (CTCAE v4.0 grade) as a part of the baseline medical history.  AEs that are serious, considered related to study treatment or the study, or that caused the patient to discontinue before completing the study should be followed until the event is resolved, the event is no longer considered to be drug-related, the event becomes stable or returns to baseline, a new treatment is initiated for the patient, or the patient dies or is lost to follow-up. Frequency of AE and SAE follow-up evaluation is left to the discretion of the investigator. Data on SAEs that occur before the end of the trial will be stored in the collection database and the Lilly Safety System.
Concomitant medication assessment		X		X	X	X	X	X		Including those medications taken within 28 days prior to the first dose of study therapy.

Procedure	Baseline Relative Day Prior to Day 1 of Cycle 1			Treatment Cycle 1 only						Comments

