	≤28	≤14	≤7	Day 1	Day 8	Day 15	Day 22	Day 29	Day 36	
Laboratory Tests										
HIV and viral hepatitis B and C screening	X*									Includes HIV and hepatitis B and C, per institutional standards. If done within 28 days prior to Cycle 1, Day 1 as part of standard of care, does not need to be repeated. * Should be done within 60 days prior to enrollment.
Hematology		X		X	X	X	X	X	X	Every week for the first 12 weeks on therapy.
Coagulation		X					X*			Evaluations performed as part of the baseline assessment do not need to be repeated on Cycle 1, Day 1, unless required in the opinion of the investigator. * Required within 14 days of planned posttreatment tumor biopsy.
Serum chemistry		X		X	X	X	X	X	X	Every week for the first 12 weeks on therapy.
CEA and CA 15-3	X									Applies only to breast cancer cohorts and if clinically applicable.
C-reactive protein assessment		X		X	X	X	X	X	X	Every week for the first 12 weeks on therapy, and every 2 weeks thereafter.
Urinalysis		X								Evaluations performed as part of the baseline assessment do not need to be repeated on Cycle 1, Day 1, unless required in the opinion of the investigator. Urinalysis evaluations will be performed at the beginning of each cycle (that is, approximately every 6 weeks following the first dose of study therapy). If urine dipstick >1+ for protein, obtain 24-hour urine collection for protein analysis.
Serum and urine myoglobin		X*		X*	X*	X*	X*	X*	X*	*As clinically indicated, if serum CK $\geq 2.5 \times$ ULN.
Tailoring biomarkers	X									10 mL of blood to be drawn for future pharmacogenetic biomarker testing.
Blood sampling for PK, PD, IG	Refer to Attachment 4 , Attachment 5 , and Attachment 6 .						All sampling indicated in Attachment 4 , Attachment 5 , and Attachment 6 is to be done only after study eligibility is met.			
Efficacy Assessments										
Imaging studies (CT/MRI)	X*								X	Radiographic assessment of tumor response should be performed prior to the start of a cycle so that results are available before the patient receives a new cycle of treatment. If done within 28 days prior to Cycle 1, Day 1, as part of standard of care, does not need to be repeated prior to the start of Cycle 1. * For patients with treated CNS metastases that are eligible for this study, a baseline MRI documenting disease stability within 60 days prior to enrollment is required.

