Procedure	Baseline Relative Day Prior to Day 1 of Cycle 1			Treatment Cycle 1 only						Comments
	≤28	≤14	≤7	Day 1	Day 8	Day 15	Day 22	Day 29	Day 36	
Bone scan	X								X*	
Breast cancer cohort: A baseline bone scan is required, except in the event that a PET scan is performed within 28 days prior to the first dose of study therapy that is negative for bone disease. Routine bone scans during treatment are not required, except in the setting of bone-only disease (no lymph node, visceral, skin, or subcutaneous metastases), or as deemed appropriate by the investigator.
 
*Prostate cancer cohort: Bone scans are required at baseline and (follow-up [posttreatment]) every 6 weeks thereafter, or as clinically indicated.
 
If done within 28 days prior to Cycle 1, Day 1, as part of standard of care, does not need to be repeated prior to the start of Cycle 1.

Tumor assessments	X								X	
Radiographic assessment of tumor response should be performed prior to the start of a cycle so that results are available before the patient receives a new cycle of treatment.
 
If done within 28 days prior to Cycle 1, Day 1, as part of standard of care, does not need to be repeated prior to the start of Cycle 1.

Tumor core needle or surgical biopsy		X							X	
Required: The first tumor biopsy will be taken (attempted) at baseline (predose), within 14 days prior to dosing on Cycle 1, Day 1, and the second tumor biopsy will be taken (attempted) within 14 days prior to dosing on Cycle 2, Day 1.
 
Optional: In cases of disease progression, if the patient's condition allows it, an optional tumor biopsy will be performed, as clinically indicated (refer to Section 8.2.2.2).

Ad hoc tumor tissue and blood sampling				X						
Optional: Additional tumor tissue and/or blood samples for biomarker research may be obtained at the investigator's discretion in discussion with the patient, such as at the time of radiographic response or treatment progression. If, at any time during the study, tumor tissue is obtained through a core biopsy, surgical biopsy, or resection as routine clinical care, the sponsor requests a tissue block or unstained slides for analysis of potentially relevant surrogate biomarkers.

Study Therapy Administration										
Administer LY3022855 Weekly (on Days 1, 8, 15, 22, 29, and 36)				X	X	X	X	X	X	
Administer LY3022855 Every 2 Weeks (on Days 1, 15, and 29)				X		X		X		

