***Special Considerations for Lesion Measurability*****Bone lesions:**

- Bone scan, positron emission tomography (PET) scan, or plain films are not considered adequate imaging techniques to measure bone lesions.
- Lytic bone lesions or mixed lytic-blastic lesions, with identifiable soft tissue components, that can be evaluated by cross sectional imaging techniques such as CT or MRI, can be considered measurable lesions if the soft tissue component meets the definition of measurability.
- Blastic bone lesions are non-measurable.

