**Table 2. Time Point Response: Patients with Nontarget Disease Only**

Nontarget Lesions	New Lesions	Overall Response
CR	No	CR
Non-CR/non-PD	No	Non-CR/non-PD a
Not all evaluated	No	NE
Unequivocal PD	Yes or No	PD
Any	Yes	PD

Abbreviations: CR = complete response; NE = inevaluable; PD = progressive disease; SD = stable disease.

a non-CR/non-PD is preferred over SD for nontarget disease.

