### Confirmatory Measurement/Duration of Response

#### *Confirmation:*

The main goal of confirmation of objective response in clinical trials is to avoid overestimating the response rate observed. The confirmation of response is particularly important in *nonrandomized trials* where response (CR/PR) is the primary end point. In this setting, to be assigned a status of PR/CR, changes in tumor measurements must be confirmed by repeat assessments that should be performed no less than 4 weeks after the criteria for response are first met. To confirm a response of CR, a full assessment of all target and nontarget lesions that were present at baseline must occur, including those measured by bone scan. To confirm a PR or SD, a full assessment of target lesions that were present at baseline must occur; assessment of nontarget lesions is not required.

However, in *randomized trial* (Phase 2 or 3) or studies where SD or progression is the primary endpoints, confirmation of response is not required. But, elimination of the requirement may increase the importance of central review to protect against bias, in particular of studies which are not blinded.

In the case of SD, follow-up measurements must have met the SD criteria at least once after start of treatment at a minimum interval not less than 6 weeks measured from first dose.

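### The disease control rate has no place for stable nontarget-only disease, and its 6-week stable-disease minimum falls after the scheduled first scan, so on schedule it acts as about 11 weeks

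*Protocol*

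**What the plan says.** **Definition.** Protocol 10.8 and SAP 6.6 both estimate DCR as the "proportion of enrolled patients who have a best overall response of CR, PR, or stable disease", with an exact 95% confidence interval if appropriate. Neither section mentions non-CR/non-PD or a minimum duration for stable disease (SD).

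**Nontarget-only disease.** Attachment 9, Table 2 lists CR, non-CR/non-PD, not evaluable and PD as the overall responses for patients without measurable disease. Its footnote reads "non-CR/non-PD is preferred over SD for nontarget disease".

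**Who can enroll.** Inclusion Criterion [1] requires that patients "Have a confirmed diagnosis of advanced, refractory breast or prostate cancer that is evaluable by radiologic testing"; it does not ask for measurable disease. Attachment 9 states "Blastic bone lesions are non-measurable". The Attachment 1 bone-scan row waives routine on-treatment scans in breast cancer "except in the setting of bone-only disease", so such patients are foreseen.

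**SD minimum.** Attachment 9 (Confirmation) requires the SD criteria to be met at least once "at a minimum interval not less than 6 weeks measured from first dose".

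**Scan schedule.** Attachment 1 marks the first on-study CT/MRI and tumor assessment under Cycle 1 Day 36 and the second under Cycle 2 Day 36. Apart from Cycle 1 Day 1, "allowable visit windows are ±3 days, unless indicated otherwise". The imaging comment adds that assessment "should be performed prior to the start of a cycle so that results are available" when the next cycle begins.

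**The concern.** Attachment 9 says that best overall response will be derived by an algorithm, so someone must code both rules. Coded as written, they score some stable patients as failures.

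A patient with stable nontarget-only disease never receives the label SD and is not counted as controlled, however long the stability lasts. A patient with measurable disease who is stable at the first scan and has progressed at the second has no assessment late enough to earn SD. A stable patient who stops for another reason before the second scan also has no scheduled scan that can earn it, because the 30-day follow-up lists no imaging.

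DCR would then look lower than a reader expects, and its summary table would not show why. With 5 or 10 patients per dosage, one reclassified patient moves the estimate visibly.

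**Working it through.** The documents state no target, power or precision for DCR, so there is no plan figure to reproduce. The check is category mapping and calendar arithmetic.

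**1. Category mapping**

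| State | Category in Attachment 9 | In DCR numerator? | In denominator? |
|---|---|---|---|
| Stable, measurable disease | SD (Table 1) | Yes, if the minimum is met | Yes |
| Stable, nontarget disease only | Non-CR/non-PD (Table 2) | Not stated | Yes, if enrolled |

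Cost of each stable nontarget-only patient left out, using the plan's own group sizes: 1/5 = 20 points (first stage of Dosage C or D), 1/10 = 10 points (full dosage cohort), 1/40 = 2.5 points (all enrolled).

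Illustration with assumed counts: 5/10 has an exact 95% interval of 18.7% to 81.3%. If two of those five are nontarget-only and are dropped from the numerator, 3/10 has an interval of 6.7% to 65.2%. The documents do not give the share of such patients.

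**2. Calendar**

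Elapsed days from first dose = study day − 1. The window is ±3 days. The minimum is 6 × 7 = 42 days.

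| Time point | Study day | Elapsed days | Window | Meets 42? |
|---|---|---|---|---|
| Cycle 1 Day 36 (first scan) | 36 | 35 | 32–38 | No; 4 to 10 days short |
| Cycle 2 Day 1 (dosing; no scan marked) | 43 | 42 | 39–45 | Only if a scan is done then, at 42 days or later |
| Cycle 2 Day 36 (second scan) | 42 + 36 = 78 | 77 | 74–80 | Yes |

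The Week 6 bone scan in Protocol 8.3 does not move the first assessment later. Attachment 1 equates Weeks 1, 2, 4 and 5 with Days 1, 8, 22 and 29, so Week 6 begins on Day 36.

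On schedule, SD is first creditable at 77 days: 77/7 = 11 weeks.

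**3. Size of the timing effect**

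The documents give no PFS figure. Assume exponential PFS, S(t) = 2^(−t/median). The loss against a rule that really operates at 42 days is S(42) − S(77), with t in days.

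| Assumed median PFS | S(42) | S(77) | Loss, points |
|---|---|---|---|
| 6 weeks (42 d) | 0.500 | 0.281 | 22 |
| 8 weeks (56 d) | 0.595 | 0.386 | 21 |
| 12 weeks (84 d) | 0.707 | 0.530 | 18 |
| 16 weeks (112 d) | 0.771 | 0.621 | 15 |
| 24 weeks (168 d) | 0.841 | 0.728 | 11 |

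This does not model irRECIST, under which some RECIST progressions count as not progressed (Protocol 5.2.2). It also ignores scans done outside the window.

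**The case against.** **The minimum can be met.** A reader might infer that no first scan can ever reach 42 days. The documents do not support that. The ±3-day window yields where something else is indicated, the imaging row carries its own timing comment, Protocol 8.3 asks for assessment every 6 weeks, and Protocol 8.4 treats collection times as targets. A predose scan on Day 43, or a scan before a delayed Cycle 2, would reach 42 days. This stands: the shortfall applies to in-window scans. It does not remove the conflict, because Attachment 1 marks Day 36, Protocol 8.3 refers to Attachment 1 for timing, and results are wanted before the next cycle.

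**The footnote may only rename SD.** Possibly the sponsor means non-CR/non-PD to count as disease control. Neither document says so, and an algorithm must code one reading.

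**Nontarget-only patients may have no RECIST response.** Protocol 6.2 and 8.3 tie RECIST and irRECIST response to measurable disease, while Table 2 assigns responses without it. This is a fair prior question. If those patients receive no RECIST response, they still remain in a denominator of all enrolled patients.

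**Size.** It is tempting to count everyone stable at 35 days and progressed by 77, which gives 28, 26, 22, 18 and 14 points for the same medians. That overstates the loss: patients who progress between 35 and 42 days are properly excluded by a 6-week rule.

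**Duration of treatment.** One might read the design as a single planned cycle, so that many stable patients never reach the second scan. Protocol 6.2 also says that treatment duration is not fixed, so stopping while stable is not the default.

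**Visibility.** The planned response listings would show non-CR/non-PD for individual patients. The DCR estimate and its interval would not.

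**Conclusion.** The plan is wrong as written on both counts, and the consequence is minor. It is confined to DCR, a secondary descriptive endpoint. The Dosage C/D continuation rule counts responders and is unaffected.

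The missing mapping for non-CR/non-PD is certain from the text. Its effect is 20, 10 or 2.5 points per affected patient for groups of 5, 10 or 40, with an unknown number of patients.

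The timing conflict holds for any first scan done in its window: a nominal 6-week criterion operates at about 11 weeks. The 22-to-11-point range rests wholly on the assumed exponential PFS and medians and is illustrative.

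A reader might conclude that the 42-day rule is an error and that 32 days is the right minimum. The documents do not support that. Attachment 9 states the 42-day rule explicitly and it can be programmed from recorded dates; a shorter minimum is a choice. What needs correcting is the mismatch between rule and schedule.

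**What to change.** 1. In Protocol 10.8 and SAP 6.6, state that a best overall response of non-CR/non-PD meeting the SD minimum interval counts as disease control. Reconcile Protocol 6.2 and 8.3 (response tied to measurable disease) with Attachment 9, Table 2, so that it is clear which patients receive a response category.

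2. Reconcile the SD minimum in Attachment 9 with the first assessment in Attachment 1 so that the two agree. In the best-overall-response algorithm, produce DCR twice and label each: once accepting the scheduled first on-study assessment for SD if done in its window (32 days or more from first dose), and once under the strict 42-day rule. Subtracting the 3-day window from 42 does not help, because 39 days is still later than the last in-window scan at 38.

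**Cost.** A sentence or two for each point and one extra DCR row per group; no new visits, scans or samples. The version that accepts the first scan is less demanding, which is why both are shown.

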## 10. Data Analyses

For this study, approximately 40 patients will be enrolled. Patients with prostate cancer will be treated at 1 of 2 dosages of LY3022855, and patients with breast cancer will be treated at 1 of 4 dosages of LY3022855. Of those enrolled patients, approximately 36 patients will be evaluable: 30 patients with advanced, refractory breast cancer and 6 patients with advanced, refractory prostate cancer. Refer to Section 6.1 for the definition of an evaluable patient.

CSF-1 is the primary pharmacodynamic biomarker documented in Study JSCA. Serum CSF-1 was quantified for 17 patients over time; that is, at baseline and 8 hours after the first infusion. All those patients had increased levels of CSF-1 at 8 hours, compared with the baseline level. The effect size (or Cohen's  $d$ ) is 5.81. Consequently, the power of observing any change between the eighth hour and baseline is close to 1 as long as the number of samples is  $\geq 3$ .

However, when the effect size is as small as 1 for the pharmacodynamic markers other than CSF-1, the power is approximately 0.159 if only 3 patients are sampled.

For Dosages C and D (patients with breast cancer), the sample size of 10 for each dosage provides a reasonable power to explore preliminary signals of efficacy. Assuming that a true best overall response rate (ORR) less than 20% indicates inadequate antitumor activity, then at a one-sided type 1 error rate of 5%, the total sample size of 10 will provide 80% power if the true best ORR is 60% or higher, using a 2-stage design method as follows. During the first stage, 5 patients will be enrolled and treated on each of Dosages C and D. If 2 or more of the 5 patients on either dosage (C or D) are observed to be responders by the end of the first stage, an additional 5 patients will be enrolled at the applicable dosage. Then, if 5 or more of the total of 10 patients at that dosage are observed to be responders by the end of the second stage, further exploration of drug efficacy is warranted for that dosage.

All data collected will be summarized using descriptive statistics or graphics, if appropriate, and will also be listed.

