5.1. Summary of Study Design

Study I5F-MC-JSCB (JSCB) is a single-center, open-label, nonrandomized, noncontrolled Phase 1 study of intravenous (IV) LY3022855 in patients with advanced, refractory breast or prostate cancer. Eligible patients will receive LY3022855 as an infusion. Study JSCB is intended to explore clinical response and immunological activity of single-agent LY3022855 in approximately 40 patients (enrolled, of whom 36 will be evaluable), by assessment of biomarkers, cytokines, and immune cells. The study schema is shown in [Figure JSCB.5.1](#).

Patients with prostate cancer

Patients with breast cancer

*Additional patients may be enrolled if marked antitumor activity is demonstrated at this dose.

Abbreviations: LY = LY3022855 (IMC-CS4); PD = progressive disease.

Figure JSCB.5.1. Study design for I5F-MC-JSCB.

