6.6. Efficacy Analyses

One of the secondary objectives of the study is to measure any antitumor activity. Thus, tumor response data will be reported using listings and descriptive statistics. The ORR is estimated by the proportion of enrolled patients who have a best overall response of complete response (CR) or partial response (PR). The disease control rate (DCR) is estimated by the proportion of enrolled patients who have a best overall response of CR, PR, or stable disease. A 95% exact confidence interval will be constructed to determine the level of precision of the ORR and DCR, if appropriate. Time-to-event variables such as progression-free survival (PFS), duration of response, and overall survival (OS) will be tabulated, if appropriate. The Kaplan-Meier method

(Kaplan and Meier 1958) will be used to estimate the survival curves, medians, and survival rates at specified time points, if applicable.

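### For Dosages C and D, the ORR estimate and its 95% interval are not matched to the two-stage, one-sided 5% design: the simple proportion is biased slightly downward, and at 5 of 10 the interval includes the 20% that the rule rejects.

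*Protocol*

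**What the plan says.** Protocol 10 (Data Analyses), repeated in SAP 5.2, gives Dosages C and D a formal screening rule for response. It fixes the null value, "Assuming that a true best overall response rate (ORR) less than 20% indicates inadequate antitumor activity", sets a one-sided type 1 error of 5%, and claims that "the total sample size of 10 will provide 80% power if the true best ORR is 60% or higher". The first stage is 5 patients per dosage: "During the first stage, 5 patients will be enrolled and treated on each of Dosages C and D". A dosage with fewer than 2 responders stops there. Otherwise 5 more patients are added, and the dosage is judged worth pursuing "if 5 or more of the total of 10 patients at that dosage are observed to be responders by the end of the second stage".

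Protocol 10.8 defines ORR as the proportion of enrolled patients with a best response of CR or PR. It gives its precision thus: "A 95% exact confidence interval will be constructed to determine the level of precision of the ORR and DCR if appropriate". SAP 6.6 matches: "A 95% exact confidence interval will be constructed to determine the level of precision of the ORR and DCR, if appropriate". Neither section mentions the two stages, an estimator suited to them, or a confidence level tied to the one-sided 5% test. SAP 6.1 describes the study's analyses as descriptive, with an exception for exploratory biomarker work, and reports them by dose group.

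**The concern.** Two features of the rule do not carry over to the reporting. First, the number of patients behind the ORR is 5 or 10 depending on the first five outcomes, and a simple proportion is not unbiased under that kind of stopping. Second, a two-sided 95% interval puts 2.5% in each tail, whereas the rule tests at one-sided 5%. A result with a p-value between 0.025 and 0.05 therefore passes the rule and still has 20% inside its interval.

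What is at stake is a clinical study report that says further exploration is warranted beside an interval that does not exclude inadequate activity, with nothing in the plan to explain why.

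**Working it through.** **Inputs** (Protocol 10; SAP 5.2): null ORR 20%, target ORR 60%, one-sided 5%, n1 = 5, continue if X1 ≥ 2, total n = 10, pass if X1 + X2 ≥ 5. The documents say only that the interval is 95% exact. I take it as the fixed-sample Clopper-Pearson interval, because no two-stage method is named.

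**1. The plan's own figures.** P(pass | p) = Σ over x1 = 2 to 5 of b(5, x1, p) × P(X2 ≥ 5 − x1), where b is the binomial probability.

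- p = 0.2: 0.2048 × 0.05792 + 0.0512 × 0.26272 + 0.0064 × 0.67232 + 0.00032 × 1 = 0.0299, within 5%.
- p = 0.6: 0.2304 × 0.68256 + 0.3456 × 0.91296 + 0.2592 × 0.98976 + 0.07776 × 1 = 0.807, against the stated 80%.

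The rule does what the plan claims.

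**2. Bias of the simple proportion.** It is X1/5 if the dosage stops and (X1 + X2)/10 if it continues. Hence bias = −E[(X1 − 5p)/10; X1 ≥ 2], which simplifies to −2p²(1 − p)⁴.

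| True ORR | Bias (points) |
|---|---|
| 20% | −2 × 0.04 × 0.4096 = −3.3 |
| 33.3% (largest) | −2 × (1/9) × (16/81) = −4.4 |
| 40% | −2 × 0.16 × 0.1296 = −4.1 |
| 60% | −2 × 0.36 × 0.0256 = −1.8 |

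**3. The boundary result, 5 of 10.** The two-stage p-value against 20% is P(pass | 0.2) = 0.0299. It is below 0.05, so the rule rejects 20%, but above 0.025. The stage-wise lower limit solves P(reach stage 2 and total ≥ 5; p) = α/2, and the upper limit solves P(stop, or total ≤ 5; p) = α/2.

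| Interval at 5 of 10 | Limits | Contains 20%? |
|---|---|---|
| 95% fixed-sample exact (as planned) | 18.7% to 81.3% | yes |
| 95% stage-wise | 19.1% to 81.6% | yes |
| 90% fixed-sample exact | 22.2% to 77.8% | no |
| 90% stage-wise | 22.8% to 78.1% | no |

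Moving to stage-wise limits at 95% does not remove the conflict; moving to 90% does. At 6 of 10 the planned 95% lower limit is 26.2%, so the conflict is confined to exactly 5 of 10.

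**4. How often that result arises.** There are 226 ways to reach 5 of 10 through stage 2 (100 + 100 + 25 + 1 for X1 = 2 to 5), so P(5 of 10) = 226 p⁵(1 − p)⁵. That is 2.4% at 20% and 18.0% at 60%. As a share of passes it is 0.0237/0.0299 = 79% at 20% and 0.180/0.807 = 22% at 60%.

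**5. Unbiased estimate at 5 of 10.** UMVUE = Σ C(4, x1−1)C(5, 5−x1) / Σ C(5, x1)C(5, 5−x1) over x1 = 2 to 5 = (40 + 60 + 20 + 1)/(100 + 100 + 25 + 1) = 121/226 = 53.5%, against the observed 50%.

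**6. Coverage of the planned interval.** Enumerating all outcomes over a fine grid of true ORR, coverage under the two-stage design never falls below about 95.8% (near ORR 0.55).

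**The case against.** The strongest reply is that the interval is not the decision tool. Antitumor activity is a secondary objective, the interval is offered for precision and only where appropriate, and the go decision uses counts. A descriptive 95% interval need not be the inverse of a one-sided 5% screen, and one level for ORR and DCR in every group has the merit of uniformity. The bias is at most 4.4 points, in cohorts whose interval at 5 of 10 is about 63 points wide, and overall it runs against the drug. All of this stands, and it limits the weight of the point. It does not make the reported ORR unbiased, and it leaves the reader of a 5-of-10 result with two statements that disagree.

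Some stronger readings are tempting, but the documents do not support them:

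- A reader might infer that ignoring the stages causes the overlap with 20%. It does not; the stage-wise 95% limit is also below 20%, and a single-stage rule of 5 of 10 (p = 0.033) would show the same overlap.
- A reader might infer that the interval is invalid under the design. Its coverage stays above 95%, so it is conservative.
- A reader might take the footnote to the design figure, "Additional patients may be enrolled if marked antitumor activity is demonstrated at this dose", as further result-driven enrolment to C and D. The figure is not shown in the text available, so the dosage it marks cannot be identified.
- A reader might say that C and D cannot be compared with A and B. No such comparison of ORR is planned.

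**Conclusion.** The point holds as a reporting inconsistency of modest weight. The simple ORR for C and D is biased downward by 3.3 points at a true 20% and by no more than 4.4 points anywhere. One passing result, 5 of 10, would be reported as a pass with an interval that includes the rejected value, because two-sided 95% does not match one-sided 5%. It would be wrong to conclude that the go rule is faulty: its error rate (0.030) and power (0.807) agree with the plan.

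The figures assume that the interval is fixed-sample, that the count rule is followed as Protocol 10 states it (Protocol 6.2 speaks more loosely of a review of clinical data), and that ORR is computed on exactly 5 or 10 patients per dosage. Protocol 10.8 counts all enrolled patients and Protocol 7.6.1 allows replacement of nonevaluable ones, so the denominator could exceed 10 and the figures would shift.

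**What to change.** In Protocol 10.8 and SAP 6.6, for Dosages C and D only, keep the observed proportion and the 95% exact interval, labelled descriptive. Beside them prespecify (a) the UMVUE of ORR under the 2-of-5, 5-of-10 design, and (b) a two-sided 90% interval by stage-wise ordering, whose lower limit agrees with the stated one-sided 5% rule. State that both are computed on the first 5 or 10 patients to whom the rule applies.

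The go rule, sample size and patient procedures do not change. The cost is a few sentences, a short exact calculation, and a second estimate and interval in the table. The two estimates can differ visibly: at 2 of 10 the UMVUE is 40.0% against 20% observed, and from 7 of 10 upward they coincide. The UMVUE removes bias over all outcomes of the design but not among dosages that pass, where the observed ORR runs high (mean 65.2% when the truth is 60%). Both are reasons to show the observed proportion as well.
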